## **5f. Sample Size Considerations**

A large trial is not justified given that adaptations need to be made to the protocol to make it appropriate for the population in this proposal. In this treatment development grant, we chose to recruit 100 subjects in the RCT conservatively estimating that 20% may be lost at follow-up, leaving 80% of subjects with complete data. This number will be sufficient to allow us to make judgments regarding feasibility and acceptability. Despite problems in the stability of effect size calculations with small samples (Kraemer et al., 2006), if a large effect size is detected between groups, this would be an indication that the experimental treatment is sufficiently innovative and that further testing in a larger trial is indicated.

We will test *planned paired comparisons* of our two groups. All power calculations are based on asymptotic results using the t test on the means of independent samples. Statistical power of rejecting the null hypothesis

at the 5% significance level was calculated. Power calculations involved generating the expected effect size and within-population standard deviations and fitting false alternative models to these data. **Table 3** summarizes statistical power to reject the null hypothesis of AIM 2 using the independent samples t test model that there is no mean difference between intervention types [PE v. IMI/FCU]. Findings reported in Preliminary Studies for adolescents with a prior history of problematic alcohol use are most relevant to the sample to be studied in this application. Effect sizes for the IMI/FCU condition effect on marijuana use compared to the IMI alone was substantial at 3 months ( $h = .61$ ) and 6 month ( $h = .46$ ) follow-ups. We also had a medium effect on heavy episodic drinking at 3 months ( $h=.57$ ) and 6 months ( $h=.59$ ). **Given that we were comparing two active treatments in REFRAME, FCU/IMI vs IMI alone, a medium effect is substantial. Therefore, we anticipate at least a medium effect in this application given that we are comparing the IMI/FCU to a less active condition, psychoeducation.**

As shown in Table 3, we have 60% power to detect an effect size of .5 or greater with 40 subjects per group for continuous variables such as number of days smoking marijuana. For power to detect the difference between two proportions (e.g., percent endorsing marijuana use at follow-up in the PE group vs. IMI/FCU group), the effect size was defined as the arcsine-transformed proportions (Cohen, 1988). Our data from REFRAME, described above, suggests a medium effect can be reasonably anticipated. **Table 4** shows power to test the null hypothesis of no difference in proportions between groups for a range of small to medium effect sizes ( $h$ ). Not surprisingly, for our proposed sample size ( $N=40$  per intervention group; 80 total), we do not have adequate power; however, we do indicate the necessary sample sizes to reach acceptable power for planned future R01s. While we do not anticipate achieving a true effect of that magnitude within this treatment development phase, we do expect to be able to generate a reasonable effect size estimate. For example, if we obtain a true effect size of 0.50, we will be aware that a sample size of 63 participants per treatment group will be needed to obtain the desired treatment effect in the full-scale clinical trial.

**Table 3. Estimated statistical power ( $=.05$ ) of rejecting null models of no mean differences between groups for substance use and sample size needed for 80% power.**

Effect size ( $d$ )*	Power with $N=40$ each group	$N^*$ in each group for 80% power
.20	.15	388
.30	.26	171
.40	.42	98
.50	.60	63

\* Based on existing literature, see text for references.

**Table 4. Marijuana Use/Heavy Volume Drinking**

Effect Size ( $h$ )*	Power for between group differences ( $N=40$ in each group)	$N^*$ per group for 80% power
.20	.23	393
.30	.38	174
.40	.56	98
.50	.72	63

\* Based on existing literature, see text for references.

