1 R34 DA0029871

**NCT01170026**

**7-1-13**

## **Study Design**

The project will begin with an open trial with 20 families to review and adapt the protocol. Then a two group randomized design will be used to test the primary hypothesis that an Individual Motivational Intervention (IMI) plus Family Check-Up (FCU) will lead to lower rates of SU and improved family management practices at follow-up among 13-16 year old adolescents in the truancy court program who report they have already begun to use substances compared to a group that receives psychoeducation (PE) plus Standard Care services provided by truancy court. Adolescents will be randomly assigned to the experimental condition (IMI/FCU) or the comparison condition (PE). All participants will complete baseline, 3 and 6 month follow-up assessments.

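### Table 4 mixes a one-sided 5% power column with a two-sided 5% sample-size column; at two-sided 5%, power at h = .50 is .61, not .72

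*Combined protocol and SAP*

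**What the plan says.** Section 5f (Sample Size Considerations) of the combined protocol and SAP gives one significance level for all its power calculations: power "at the 5% significance level was calculated". It does not say one-sided or two-sided.

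- **Table 3 (continuous outcomes, effect size d = .20/.30/.40/.50).** Power with 40 per group is .15/.26/.42/.60, and N per group for 80% power is 388/171/98/63. The text repeats the last power value: "we have 60% power to detect an effect size of .5 or greater with 40 subjects per group for continuous variables".
- **Table 4 (marijuana use and heavy drinking as proportions, h = .20/.30/.40/.50).** Under "Power for between group differences ( $N=40$ in each group", power is .23/.38/.56/.72. N per group for 80% power is 393/174/98/63. The text says that this table "shows power to test the null hypothesis of no difference in proportions between groups" and that "the effect size was defined as the arcsine-transformed proportions".
- **Carried forward.** For an effect of 0.50, "a sample size of 63 participants per treatment group will be needed" in the later full-scale trial.
- **Stated limit.** At 40 per group, "we do not have adequate power; however, we do indicate the necessary sample sizes" for later studies.

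The hypothesis under Study Design is directional: the intervention "will lead to lower rates of SU and improved family management practices at follow-up".

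**The concern.** The conflict shows before any calculation. At an effect size of .50 both tables ask for 63 per group to reach 80% power. At 40 per group, Table 3 gives .60 and Table 4 gives .72. Two tests that need the same N for the same power at the same standardized effect should have nearly the same power at any other N.

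As printed, the binary substance-use outcomes look clearly better powered than the continuous ones. The row that matters most is .50, because section 5f expects at least a medium effect. There, .72 looks close to the 80% target, with a type II error risk of 28%. At .61 the risk is 39%. Section 5f is meant to inform later trials, so the difference could affect which outcome is chosen next, or how a null result here is read.

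**Working it through.** **Inputs.** 40 per group and h = .20/.30/.40/.50 (Table 4), a 5% level (section 5f text) and an 80% target (Table 4 heading). Sidedness is not stated, so both versions are computed. Dropout is already reflected in the 40 per group (100 × .8 = 80, in two groups).

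**Formulas** (normal approximation; the difference on the arcsine scale has unit SD per observation):

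- Noncentrality δ = h × √(n/2). With n = 40, δ = h × √20 = .894, 1.342, 1.789, 2.236.
- Power, one-sided 5%: Φ(δ − 1.645).
- Power, two-sided 5%: Φ(δ − 1.960) + Φ(−δ − 1.960). The second term matters only at h = .20.
- N per group for 80% power: 2 × (z + .842)² / h², with z = 1.645 or 1.960.

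**Step 1: reproduce the power column (n = 40 per group).**

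| h | Table 4 | One-sided 5% | Two-sided 5% | Stated minus two-sided (points) |
|---|---|---|---|---|
| .20 | .23 | .2265 | .1455 | 8.5 |
| .30 | .38 | .3809 | .2687 | 11.1 |
| .40 | .56 | .5573 | .4322 | 12.8 |
| .50 | .72 | .7228 | .6088 | 11.1 |

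All four entries match one-sided 5% to two decimals, and none matches two-sided 5%. At h = .50, for example, Φ(2.236 − 1.645) = Φ(.591) = .723, while Φ(2.236 − 1.960) = Φ(.276) = .609. Solving each stated power for alpha gives .0512/.0498/.0507/.0491 one-sided, or about .10 two-sided in every row.

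**Step 2: reproduce the N column (80% power).**

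| h | Table 4 | Two-sided 5% | One-sided 5% |
|---|---|---|---|
| .20 | 393 | 392.4 | 309.1 |
| .30 | 174 | 174.4 | 137.4 |
| .40 | 98 | 98.1 | 77.3 |
| .50 | 63 | 62.8 | 49.5 |

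All four entries match two-sided 5% to within one participant, and none matches one-sided 5%. At the one-sided alpha of the power column, the stated Ns would give power of .877/.876/.876/.877, not .80.

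**Step 3: rule out other explanations.**

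- *A different n.* To give the four stated powers, two-sided 5% would need about 74, 61, 56 and 52 per group, so no single n fits. With 50 per group (no dropout) power is .169/.323/.516/.705, which comes close only in the last row.
- *A different test.* The t test at n = 40, effect .50, two-sided, gives .598 against .609 by the normal approximation. That is about one point of the 12-point gap.
- *Raw proportions.* The pooled two-proportion formula at h = .50, with control rates of 50%, 70% and 90% (assumed, since the plan gives none), yields two-sided power of .60, .60 and .59.

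**Step 4: compare with Table 3.** The two-sided t test at 40 per group gives .143/.263/.424/.598, against .15/.26/.42/.60 stated. The one-sided version gives .224/.376/.551/.716. Table 3's power column is therefore two-sided, with small rounding or method differences.

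**The case against.** The best defence is that sidedness is never declared and the study hypothesis is directional. A one-sided 5% test would be a legitimate choice, and the power column would then be right. The text also uses the columns differently: power describes this trial, and N serves later trials. A different convention for each is conceivable. However, the plan does not say so, and Table 3's power column describes this same trial on a two-sided basis. A one-sided reading also moves the error without removing it: Table 4's N column, Table 3, and the 60% and 63 in the text would all become wrong.

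A second objection is that nothing depends on the error, and much of this stands. The plan concedes inadequate power, which is true at .72 and at .61. The 100 families are justified by feasibility and acceptability, the analysis plan puts its emphasis on effect sizes, and the text never quotes .72.

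A third objection is that Table 3 is not a perfect benchmark, and this also stands. Its Ns of 388 and 171 fall slightly below the two-sided 392.4 and 174.4. At 171 per group, two-sided power is .792. Its .15 at d = .20 fits the normal approximation (.146) better than the t test (.143). These gaps are far too small to explain Table 4.

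**Conclusion.** The concern holds. No single alpha reproduces both columns of Table 4, and this needs no assumption about what was intended, since each column matches in all four rows under opposite conventions.

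The statement that power is overstated rests on one inference: that two-sided 5% is the working convention. Table 3's power column, both N columns and the 63 per group support it. On that basis, power for the binary outcomes at 40 per group is .15/.27/.43/.61 against .23/.38/.56/.72 stated.

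If one-sided 5% was intended, Table 4's power column stands. Its N column would then be about 310/138/78/50, and Table 3's power about .22/.38/.55/.72.

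This should be corrected, but it does not alter the trial's size, the 63 per group (correct for two-sided 5%) or the admission that power is inadequate.

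**What to change.** State two-sided 5% in the headings of Tables 3 and 4, and replace Table 4's power column with .15, .27, .43 and .61. The N column of Table 4, the 60% and the 63 per group in the text, and Table 3's power column can stay. Table 3's 388 and 171 could be tidied in the same edit (392.4 and 174.4 by the formula above).

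If a one-sided test was intended, say so and give the reason. Then recompute Table 4's N column (about 310/138/78/50), Table 3, and the 60% and 63 in the text on the same basis.

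The cost of the first route is two headings and four table entries. The stated power becomes less favourable, and no further families are needed.
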